8.2.4 Anxiety Symptoms Questionnaire

The Anxiety Symptoms Questionnaire (ASQ) is a brief self-report questionnaire which measures frequency and intensity of symptoms and was developed to improve assessment of anxiety symptoms in a clinical setting. The ASQ will be performed at timepoints outlined in [Section 1.3](#), after completion of all other simultaneously scheduled procedures to avoid interference with scheduled vital sign, ECG, and PK evaluation.

Instructions will be provided to participants related to completing each questionnaire.

8.2.5 Clinical Safety Laboratory Tests

See [Table 6](#) in [Section 10.2](#) for the list of clinical laboratory tests to be performed and the SoA ([Section 1.3](#)) for the timing and frequency.

Local laboratories will be utilized to process and provide results for clinical laboratory tests allowing for immediate participant medical management. The Investigator must review the laboratory report, document this review, and record any clinically significant changes occurring during the study as an AE. All AEs require appropriate follow-up as described in Section 8.3). The laboratory reports must be filed with the source documents.

All laboratory tests with values considered abnormal and clinically significant from the time of study treatment administration to the end of the study should be repeated up to or until the values return to normal or baseline, or are no longer considered clinically significant by the Investigator or medical monitor. If clinically significant values do not return to normal/baseline within a period of time judged reasonable by the Investigator, the etiology should be identified, and the Sponsor notified.

All protocol-required laboratory tests, as defined in [Table 6 \(Section 10.2\)](#), must be conducted in accordance with the Laboratory Manual and the SoA ([Section 1.3](#)).

If laboratory values from non-protocol-specified laboratory tests performed at the institution's local laboratory require a change in participant management or are considered clinically significant by the Investigator (e.g., SAE or AE or dose modification), then the results must be recorded.

8.2.6 Pregnancy Testing

Women of nonchildbearing potential should only be included after a negative highly sensitive serum pregnancy test at screening and urine pregnancy test prior to study treatment administration.

Additional urine pregnancy testing should be performed at times specified in the SoA ([Section 1.3](#)) and when pregnancy is otherwise suspected during the study.

8.2.7 Medical History/Demographics

Surgical, and general medication history will be recorded in the eCRF. Medical history will include COVID-19 infection and treatments received, COVID-19 vaccination status (including date and vaccine type received).

8.3 Adverse Events, Serious Adverse Events, and Other Safety Reporting

The definitions of AEs and SAEs can be found in [Section 10.3](#).

Adverse events will be reported by the participant (or, when appropriate, by a caregiver, surrogate, or the participant's legally authorized representative).

The Investigator and any qualified designees are responsible for detecting, documenting, and recording events that meet the definition of an AE or SAE and remain responsible for following up on all AEs (see Section 8.3.3).

The method of recording, evaluating, and assessing causality of AEs and SAEs and the procedures for completing and transmitting SAE reports are provided in [Section 10.3](#).

8.3.1 Time Period and Frequency for Collecting AE and SAE Information

All SAEs will be collected from the signing of the ICF until the last study visit at the timepoints specified in the SoA ([Section 1.3](#)). All AEs will be collected from the start of study treatment until the last study visit at the timepoints specified in the SoA ([Section 1.3](#)).

Medical occurrences that begin before the start of obtaining informed consent will be recorded as medical history/current medical conditions, not as AEs. All SAEs will be recorded and reported to the Sponsor or designee immediately and under no circumstance should this exceed 24 hours of the Investigator's awareness of the event, as indicated in [Section 10.3](#). The Investigator will submit any updated SAE data to the Sponsor or designee within 24 hours of their awareness of the updated information.

Investigators are not obligated to actively seek information on AEs or SAEs after conclusion of the study participation. However, if the Investigator learns of any SAE, including a death, at any time after a participant has been discharged from the study, and he/she considers the event/cause of death to be reasonably related to the study treatment or study participation, the Investigator must promptly notify the Sponsor or designee.

The method of recording, evaluating, and assessing causality of AE and SAE and the procedures for completing and transmitting safety reports are provided in [Section 10.3](#).

8.3.2 Method of Detecting AEs and SAEs

Care will be taken not to introduce bias when detecting AEs and/or SAEs. Open-ended and nonleading verbal questioning of the participant is the preferred method to inquire about AE occurrences.

8.3.3 Follow-up of AEs and SAEs

After the initial AE/SAE report, the Investigator is required to proactively follow each participant at subsequent visits/contacts. All AEs will be followed until resolution, stabilization, the event is otherwise explained, or the participant is lost to follow-up (as defined in [Section 7.3](#)). Further information on follow-up procedures is provided in [Section 10.3](#).

8.3.4 Regulatory Reporting Requirements for SAEs

Prompt notification by the Investigator to the Sponsor of an SAE is essential so that legal obligations and ethical responsibilities toward the safety of participants and the safety of a study treatment under clinical investigation are met.

The Sponsor has a legal responsibility to notify both the local regulatory authority and other regulatory agencies about the safety of a study treatment under clinical investigation.

An Investigator who receives an Investigator safety report describing an SAE or other specific safety information (e.g., summary or listing of SAEs) from the Sponsor will review and then file it along with the IB and will notify the Institutional Review Board (IRB), if appropriate according to local requirements.

Investigator safety reports must be prepared for suspected unexpected serious adverse reactions (SUSARs) according to local regulatory requirements and Sponsor policy and forwarded to Investigators as necessary.

8.3.5 Pregnancy

Details of all pregnancies in female participants and, if indicated, female partners of male participants will be collected after the start of study treatment and until 10 weeks after dosing with study treatment. If a pregnancy is reported, the Investigator will record pregnancy information on the appropriate form and submit it to the Sponsor or designee within 24 hours of learning of the female participant or female partner of male participant pregnancy and should follow the procedures outlined in [Section 10.4](#).

While pregnancy itself is not considered to be an AE or SAE, any pregnancy complication (or elective termination) of a pregnancy for medical reasons will be reported as an AE or SAE.

If the outcome of the pregnancy meets the criteria for immediate classification as an SAE (i.e., spontaneous abortion, stillbirth, neonatal death, or congenital anomaly [including that in an aborted fetus, stillbirth, or neonatal death]), the Investigator will report according to the SAE reporting procedures described in [Section 10.3](#).

The participant/pregnant female partner will be followed to determine the outcome of the pregnancy e.g., until delivery of baby or for longevity. The Investigator will collect follow-up information on the participant/pregnant female partner and the neonate and the information will be forwarded to the Sponsor or designee.

Any post-study pregnancy-related SAE considered reasonably related to the study treatment by the Investigator will be reported to the Sponsor as described in Section 8.3.4. While the Investigator is not obligated to actively seek this information in former study

participants/pregnant female partner, he or she may learn of an SAE through spontaneous reporting.

Any female participant who becomes pregnant after the single dose administration of study treatment, may continue participating in the study to complete required assessments until Follow-up/EOS Visit.

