4.0 STUDY DESIGN

4.1 Overall Design

This is a Phase 1a, single center, double-blind, placebo-controlled, randomized, single ascending-dose first-in-human (FIH) study. The study will recruit up to 40 healthy normal participants, aged 18 to 55 years inclusive, with standard inclusion/exclusion criteria for healthy participant studies. Up to 5 cohorts of 8 participants (6 active, 2 placebo participants per cohort) will be enrolled with each participant assigned to receive a single dose of CS-1103 or placebo on 1 occasion (Day 1).

All participants will be screened within 28 days of dose administration and participants will check-in to the inpatient clinical research unit (CRU) on Admission/Day –1. Participants will be randomized on Day –1, the day prior to their schedule CS-1103 administration (after meeting all eligibility criteria). Participants are scheduled to remain in the CRU for up to 48 hours postdose for safety and PK assessments. Participants will be discharged on Day 3 after completion of all scheduled assessments and will be asked to return to the CRU on Day 8 for the end of study (EOS) visit. Note: Discharge from the CRU may be delayed for up to 8 hours to optimize PK assessment (see [Section 8.4.1](#)). The study duration will be approximately 37 days.

All participants for a dose level may check-in to the CRU on the same date. However, each dose level will include 2 sentinel participants (1 active, 1 placebo) who will be dosed first and monitored by an Investigator for a minimum of 24 hours. The available safety and tolerability data from the sentinel participants, up to 24 hours post dose, will be reviewed by an Investigator. Following this safety data review, dosing of the remaining participants in the cohort may proceed (see [Section 10.1.7.1](#)). The remaining participants for each dose level will be randomized the day prior to dosing and will dose on Day 1, provided there are no safety or tolerability concerns, using a 5:1 randomization ratio to active or placebo study treatment separately for each dose level. A randomization list will be prepared for each cohort. See [Section 4.5](#) for dose escalation details.

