5.1 Inclusion Criteria

Participants are eligible to be included in the study only if all of the following criteria apply:

1. Provision of signed and dated, written informed consent prior to any study specific procedures.
2. Healthy male and/or female participants aged 18 to 55 years, inclusive.
3. A body mass index between 18.0 to 30.0 kg/m², inclusive, and a minimum body weight of 50 kg.
4. Females must be of nonchildbearing potential, must not be lactating, must have a negative serum pregnancy test at the Screening Visit, and must have a negative urine pregnancy test on admission to the study site CRU. The nonchildbearing potential of the female participant will be confirmed at the Screening Visit by fulfilling 1 of the following criteria (see [Section 10.4.1](#) for additional information):
 - Postmenopausal defined as amenorrhea for at least 12 months following cessation of all exogenous hormonal treatments and with follicle stimulating hormone (FSH) levels in the laboratory defined postmenopausal range.
 - Documentation of irreversible surgical sterilization by hysterectomy, bilateral oophorectomy or bilateral salpingectomy but not tubal ligation.
5. Male participants should be willing to use double barrier contraception, i.e., condoms and spermicide, from the day of dosing until at least 90 days after dosing with the study treatment (see [Section 10.4.2](#) for additional information).
6. Male participants must agree not to donate sperm from the day of dosing until at least 90 days after dosing with the study treatment.
7. Considered generally healthy upon completion of medical history, physical examination, vital sign measurements, ECG, and clinical laboratory test results in the opinion of an Investigator at Screening and Admission/Day -1.
8. Must agree to abstain from alcohol intake 48 hours before administration of the study treatment, during the confinement period of the study until after the final Follow-up/EOS Visit.
9. Able to comply with the protocol and attend all scheduled visits.

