10.4.2 Contraception Guidance

Male Participants

The following text is required ONLY until it has been determined that WOCBP who are partners of male participants no longer need protection from potential exposure to study treatment in seminal fluid and should be provided by the Sponsor and/or medic. For genotoxic study treatment, or for non-genotoxic study treatment with demonstrated or suspected human teratogenicity/fetotoxicity at subtherapeutic exposure levels where it is theoretically possible that relevant systemic concentrations may be achieved in WOCBP from exposure to seminal fluid, to prevent exposure of an embryo/fetus, the following text is required.

- Male participants with female partners of childbearing potential are eligible to participate if they agree to ONE of the following during the protocol-defined time frame in **Section 5.1:**
 - Are abstinent from penile-vaginal intercourse as their usual and preferred lifestyle (abstinent on a long-term and persistent basis) and agree to remain abstinent for duration of study and at least 90 days after dosing with the study treatment.

- Agree to use a male condom with spermicide and have their partner use a contraceptive method with a failure rate of <1% per year when having penile-vaginal intercourse with a WOCBP who is not currently pregnant.
- In addition, male participants must refrain from donating sperm for the duration of the study and for at least 90 days after dosing with the study treatment.
- Male participants with a pregnant or breastfeeding partner must agree to remain abstinent from penile-vaginal intercourse or use a male condom during each episode of penile penetration from the day of dosing until at least 90 days after dosing with the study treatment.

Female Participants

Female participants of childbearing potential are not eligible to participate.

Pregnancy Testing:

- Pregnancy testing should be performed at times specified in the SoA ([Section 1.3](#)) and as required locally.
- Additional pregnancy testing may be performed at any time during the study based on an Investigator's discretion when pregnancy is suspected.
- Pregnancy testing, with a sensitivity of 5 mIU/mL will be performed using the test kit approved by the Sponsor and in accordance with instructions provided in its package insert.

Collection of Pregnancy Information

Male Participants With Partners Who Become Pregnant

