- The Investigator will attempt to collect pregnancy information on any male participant's female partner who becomes pregnant while the male participant is in this study. This applies only to male participants who receive CS-1103.
- After obtaining the necessary signed informed consent from the pregnant female partner directly, the Investigator will record pregnancy information on the appropriate form and submit it to the Sponsor or designee within 24 hours of learning of the partner's pregnancy. The female partner will also be followed to determine the outcome of the pregnancy. Information on the status of the mother and child will be forwarded to the Sponsor. Generally, the follow-up will be no longer than 6 to 8 weeks following the estimated delivery date. Any termination of the pregnancy will be reported regardless of fetal status (presence or absence of anomalies) or indication for the procedure.

Female Participants Who Become Pregnant

- The Investigator will collect pregnancy information on any female participant who becomes pregnant while participating in this study. Information will be recorded on the appropriate form and submitted to the Sponsor or designee within 24 hours of learning of a

participant's pregnancy. The participant will be followed to determine the outcome of the pregnancy. The Investigator will collect follow-up information on the participant and the neonate and the information will be forwarded to the Sponsor or designee. Generally, follow-up will not be required for longer than 6 to 8 weeks beyond the estimated delivery date. Any termination of pregnancy will be reported, regardless of fetal status (presence or absence of anomalies) or indication for the procedure.

- While pregnancy itself is not considered to be an AE or SAE, any pregnancy complication will be reported as an AE or SAE. If the outcome of the pregnancy meets the criteria for immediate classification as an SAE (i.e., spontaneous abortion, stillbirth, neonatal death, or congenital anomaly [including that in an aborted fetus, stillbirth, or neonatal death]), the Investigator will report according to the SAE reporting procedures described in [Section 10.3](#).

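### The two pregnancy-collection windows disagree, both end before the protocol's own 90-day male contraception period, and partner collection depends on an arm that the blinded site cannot see

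*Protocol*

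**What the plan says.** Four parts of the protocol bear on this.

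- **Section 8.3.5 (Pregnancy).** Details of pregnancies in female participants and, where indicated, in partners of male participants "will be collected after the start of study treatment and until 10 weeks after dosing with study treatment". No treatment arm is mentioned. The site is then referred to Section 10.4 for procedures.
- **Section 10.4.2 (Collection of Pregnancy Information).** For men, the investigator tries to collect information on any "female partner who becomes pregnant while the male participant is in this study. This applies only to male participants who receive CS-1103". For women, collection covers any "female participant who becomes pregnant while participating in this study".
- **Section 4.1 and the schedule of activities.** Participants "will be asked to return to the CRU on Day 8 for the end of study (EOS) visit", with a window of one day either side. No later contact is scheduled.
- **Section 5.1 (inclusion criteria 5 and 6) and Section 10.4.2.** Men use contraception and do not donate sperm "from the day of dosing until at least 90 days after dosing with the study treatment". Section 10.4.2 repeats the period: "male participants must refrain from donating sperm for the duration of the study and for at least 90 days after dosing".

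The trial is double-blind. Under Section 6.3 the investigator may break the code in a medical emergency, sponsor safety staff may unblind for an SAE, and the Safety Review Committee may unblind a participant or a cohort during its data review. The SAP (Section 4.2) places the final analysis after database lock and unblinding.

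**The concern.** A site that reads Section 8.3.5 keeps collecting for 10 weeks. A site that follows the procedure it is sent to stops at about one week. Neither period reaches the end of the time during which the protocol asks men to take precautions on their partners' behalf.

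The restriction to CS-1103 recipients adds a second problem. Both sections require the pregnancy form within 24 hours of the site learning of the pregnancy. At that moment a blinded investigator does not know whether the man is covered.

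What is at stake is completeness of safety capture in a first-in-human trial. Enrolled women must be of nonchildbearing potential, so in practice a pregnancy is most likely to arise in a male participant's partner. A pregnancy that is never recorded is not followed to its outcome. No primary, secondary or exploratory endpoint is affected.

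**Working it through.** This is calendar arithmetic on the protocol's own figures. No power or sample-size calculation is involved.

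**Step 1. Put the windows on one scale, in days after dosing.** Dosing is on Day 1, so Day *d* falls *d* − 1 days after dosing.

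| Rule | Ends (days after dosing) | Short of 90 days by | Share of 90 days |
|---|---|---|---|
| Section 8.3.5, 10 weeks | 10 × 7 = 70 | 90 − 70 = 20 | 20/90 = 22% |
| Section 10.4.2, last visit on Day 7 | 6 | 84 | 93% |
| Section 10.4.2, last visit on Day 8 | 7 | 83 | 92% |
| Section 10.4.2, last visit on Day 9 | 8 | 82 | 91% |

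The Section 10.4.2 rows assume that being in the study ends at the Day 8 (±1) visit.

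**Step 2. Conception date or report date.** Section 8.3.5 does not say which date must fall within the 10 weeks. If it is the report date, the delay from conception to report also counts. The documents give no such delay, so these values are assumptions:

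- 14 days: conception by day 70 − 14 = 56, leaving 90 − 56 = 34 days uncovered.
- 28 days: conception by day 42, leaving 48 days uncovered.
- 42 days: conception by day 28, leaving 62 days uncovered.

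**Step 3. Can the arm restriction be applied?** Allocation is 6 active to 2 placebo in each cohort, so 6/8 = 75% of participants receive CS-1103 (30 of 40 if all five cohorts enrol). The sex mix is not stated, so this is a ratio of participants, not of men. It does not tell the site which man is which. The stated unblinding routes compare as follows with an uncomplicated partner pregnancy:

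- Investigator code break: needs a medical emergency.
- Sponsor safety staff: needs an SAE, and Section 8.3.5 says that pregnancy in itself is neither an AE nor an SAE.
- Safety Review Committee: tied to its evaluation of study data.
- Unblinded pharmacy delegate: mentioned only for numbering replacement participants.

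None of these is provided for this purpose.

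**Step 4. Order of magnitude.** Assume that all 30 active participants are men with fertile partners, and that conception runs at 1% per year (the ceiling that Section 10.4.2 sets for the partner's method) to 5% per year (an assumption).

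- 20-day gap: 30 × 20/365 = 1.64 man-years, so 0.016 to 0.08 conceptions.
- 83-day gap: 30 × 83/365 = 6.82 man-years, so 0.07 to 0.34 conceptions.

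The expected number is small on either reading.

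**The case against.** The best defence has four parts.

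**Contraception and collection are different things.** A reader might infer that three windows contradict one another. They do not. Only Sections 8.3.5 and 10.4.2 prescribe collection, and only those two conflict. The 90 days is a precaution period that both fall short of. A reader might also take it as an established reproductive-risk window. The visible text does not support that: the rationale in Section 10.4.2 is conditional, depending on properties of the drug that no visible passage says CS-1103 has, and parts of the background and dose justification are not visible in the public version. The 90 days is used here only as the protocol's own figure. This part of the objection stands.

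**There is a backstop.** Section 8.3.5 requires a post-study pregnancy-related SAE that the investigator considers reasonably related to be reported, and it mentions the pregnant partner. Spontaneous abortion, stillbirth, neonatal death and congenital anomaly are all classed as SAEs. It would therefore be wrong to say that such conceptions will be missed. But the duty is passive, covers only events judged related, and depends on the site happening to hear of them. It narrows the gap without closing it.

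**The sections can be read together.** Section 8.3.5 expressly goes beyond the last visit, so the shortfall might be put at days 71 to 90 only. That is a reasonable reading, and it is why the larger figure is given only for Section 10.4.2 read alone. Nothing in the text says which section prevails.

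**The site is not forced to guess or unblind.** A reader might infer that it is. Section 10.4.2 limits what the investigator must attempt and does not bar collecting for every man and sorting by arm later. That is correct, but no section tells the site to do so.

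**Conclusion.** The concern holds in a limited form. Sections 8.3.5 and 10.4.2 give contradictory collection windows. Both are shorter than the protocol's own male precaution period: by 20 of 90 days (22%) under Section 8.3.5, and by 82 to 84 of 90 days (91% to 93%) under Section 10.4.2 alone. Section 10.4.2 also carries an arm restriction that blinded staff cannot apply and that Section 8.3.5 does not contain.

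Partner pregnancies conceived within the precaution period can therefore go unrecorded. Contraception is required throughout that period and the trial has at most 40 participants, so this is a weakness in safety capture that should be corrected, not a threat to the trial's conclusions.

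The day counts rest on study participation ending at Day 8 ±1. The wider gaps in Step 2 rest on an assumed reporting delay, and the expected counts in Step 4 on assumed conception rates. The 90 days applies to men only, so the shortfall concerns partner pregnancies. For female participants the defect is only that the two sections disagree. No view is taken on how long contraception should last.

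**What to change.** - Give Sections 8.3.5 and 10.4.2 one partner-pregnancy window, defined by conception date: from dosing to the end of the protocol's own male contraception period, whenever the pregnancy is reported.
- Delete the sentence in Section 10.4.2 that limits partner collection to CS-1103 recipients. Collect for all dosed male participants and assign arm at unblinding. Remove or define the qualifier in Section 8.3.5 that makes partner collection depend on being indicated.
- At the existing Day 8 visit, tell male participants how to report a partner's pregnancy, and until when.
- For female participants, make the two sections agree.

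**Cost.** This is a protocol wording change, which needs IRB approval under Section 10.1.1, and one instruction at a scheduled visit. No visit or test is added. The reporting line stays open longer. In the rare case of a pregnancy in a placebo recipient's partner, the site would have to seek her signed consent and collect health data although the man was not exposed to the drug. That burden is real but small.
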